If a participant is unable to read, an impartial third party witness will have to be present during the consent process to confirm that the process has taken place. The consent document must be read to the participant and the process documented in the research file. The participant will "make their mark" (f.ex. thumbprint) on the signature section of the consent document, in order to document their understanding. Both the witness and the person obtaining informed consent. Both the witness and the person obtaining informed consent must also sign and date the consent.

RCT Treatment randomization: After obtaining written, informed consent and following all screening and study baseline procedures, individuals in the RCT will be randomized on a 1:1 basis to participate in either TEAM or ETAU. Block randomization with block sizes ranging randomly between 4 and 8 consecutive patients will be employed to ensure that equal numbers of TEAM and ETAU patients occur within strata and are balanced with respect to relevant comorbidity (diabetes and previous stroke). The randomization list will be computer-generated by personnel within the biostatistics core of the CWRU Neurological and Behavioral Outcomes Center who are not members of the study staff.

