Quantitative data Analysis: Preliminary descriptive analyses will examine change over time in systolic BP as well as secondary outcomes. The measures of interest are valid and reliable, and have been used in stroke studies in the SSA setting.^{24, 30, 88, 97, 98} Primary and secondary outcome measurements will be assessed at baseline prior to randomization to either TEAM or ETAU, and at the 13 week and 6 month time-points using the same methods as in our pilot work. Of primary interest is the treatment by time interaction in systolic BP, measured from baseline to 6 months after randomization between TEAM and ETAU. Explanatory variables will include age, gender, stroke history and rural vs. urban status.

The 13-week systolic BP measurement will reflect the period following baseline (when individuals participating in TEAM Uganda will have just completed the “intensive” group sessions), and it will be used to assess for within-subject differences from baseline to 13 weeks and 13 week to 6-month time periods. This will allow for a greater understanding of the time course for when the expected reductions occur in the TEAM Uganda group, which we expect to mostly occur after the “intensive” group sessions have ended. We will analyze change from baseline to 13 weeks as well, analyzing contrasts within the mixed model framework.

For aim 2, we will use 2 group by 3 time waves repeated measures analysis of variance (RMANOVA) for each of the 3 hypotheses in Aims 2. These analyses will compare two groups (TEAM intervention vs. enhanced treatment as usual (ETAU)) across three time waves of systolic BP (H1), serum cholesterol (H2), and serum HbA1c (H3). When using a repeated measures ANOVA, it not only assesses mean differences across time, but also assesses group differences, as well as, the interaction of time X group which will allow us to test the trend of the means over time across the three groups. The repeated measures ANOVA, not only can be used to determine if there are mean differences across the three time periods, it can also utilize orthogonal polynomial contrasts to determine linear and quadratic trends of the means across time. Orthogonal polynomials are weights

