Sample size calculations: From our pilot data, mean baseline systolic BP was 162.9 (SD 25.6). Change from baseline to 6 months with the TEAM Uganda intervention saw a mean systolic BP of 149.7 (SD 22.1). Reductions BP of ≥ 2 mm Hg can significantly reduce the incidence of cardiovascular disease and its complications in both hypertensive and normotensive individuals, and reductions of the magnitude seen in this team's pilot work is well above thresholds that are considered clinically meaningful.^{94, 95} Our projected sample size is n=246, with 123 participants per arm. Based on our preliminary mixed model, we observed difference in systolic BP from baseline to 24 weeks of 13.22, with standard deviation of 25.84, and within subject correlation parameter value of 0.57. However, we will conservatively estimate our sample size based upon a difference of 10 mmHg, commensurate with a meta-analysis that used this magnitude of change in BP across a large sample with varying baseline blood pressure levels and comorbidities.⁹⁶ Also in our pilot work with the TEAM Uganda study, we observed an attrition rate of 12.5% at 6-months follow-up. Conservatively, for this study, we will assume 25% attrition. Finally, to assume for two-sided test of time-by-treatment group interaction, Type I error level is 0.05. Then, in a linear mixed model with subject-level and center-level random effects, power is 0.80 for a clinically significant difference of 10.0 mm Hg between treatment arms for the projected sample size of 246 subjects in total. We should thus have sufficient power. We do assume compound symmetry over the 3 time periods. We will also consider an AR(1) covariance model, and compare model fits.

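### Diabetes is balanced at randomisation but missing from the listed H1 covariates, and site is in the power model but not in the described H1 analysis

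*Combined protocol and SAP*

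**What the plan says.** The RCT Treatment randomization paragraph describes 1:1 allocation in random blocks of 4 to 8, so that "equal numbers of TEAM and ETAU patients occur within strata and are balanced with respect to relevant comorbidity (diabetes and previous stroke". Diabetes and previous stroke are the only factors named. The word strata is not defined, and site is neither included nor excluded.

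The Data Analysis Plan (Quantitative data Analysis) makes the treatment-by-time interaction in systolic BP the effect of primary interest and states: "Explanatory variables will include age, gender, stroke history and rural vs. urban status". Of the two balancing factors, previous stroke is kept and diabetes is not listed. For Aim 2 the same section describes a 2-group by 3-wave repeated-measures ANOVA, with no site or stratum term.

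The Sample size calculations rest on a different model. Power is computed "in a linear mixed model with subject-level and center-level random effects". The paragraph on secondary outcomes also refers to a primary mixed model.

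Site is a structural feature of the trial. There are three hospitals, TEAM runs in groups of 6 to 8 in participants' own clinics, and nurse and peer-educator interventionists are located at each site.

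**The concern.** A factor used to balance the arms should normally be in the primary model. Balancing removes that factor's contribution from the true variability of the treatment contrast. An analysis that omits it still counts the contribution as noise, so the reported standard error is larger than the real one. On the listed covariates this applies to diabetes.

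Site raises a separate issue. If it is not a stratum, arm numbers within a hospital are left largely to chance, and hospitals that differ in BP change can move the estimate a little in a given trial. Omitting site then costs precision and leaves that imbalance unadjusted, but the standard error is not miscalibrated. If site is a stratum, omitting it acts as omitting diabetes does.

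At stake are some precision in H1, and whether a reader can tell from the protocol how patients were allocated and which model tests the primary hypothesis.

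**Working it through.** **1. The plan's own figure.** Inputs from Sample size calculations: "two-sided test of time-by-treatment group interaction, Type I error level is 0.05"; "power is 0.80 for a clinically significant difference of 10.0 mm Hg between treatment arms"; an estimate "with standard deviation of 25.84, and within subject correlation parameter value of 0.57"; "We do assume compound symmetry over the 3 time periods"; "we will assume 25% attrition"; 123 per arm.

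- SD of change = 25.84 × √(2 × (1 − 0.57)) = 23.96.
- n per arm = 2 × (1.960 + 0.842)² × 23.96² / 10² = 90.1, so 91. Dividing by 0.75 gives 121.3, so 122 per arm and 244 in total, against 246 planned.
- With 123 × 0.75 = 92.25 completers per arm, SE = 23.96 × √(2/92.25) = 3.53 mm Hg and power = Φ(10/3.53 − 1.96) = 0.809, against 0.80 stated.

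The sample size reproduces. It does not depend on the point made here.

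**2. Omitting a balanced factor (diabetes).** Let R² be the share of variance in BP change that the factor explains. The documents give no value, so 1% to 5% is assumed. The reported SE is too wide by 1/√(1 − R²), and the true two-sided type I error is 2 × (1 − Φ(1.96/√(1 − R²))).

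| Assumed R² | SE too wide by | True type I error | Power after adjustment |
|---|---|---|---|
| 1% | 0.5% | 0.049 | 0.813 |
| 5% | 2.6% | 0.044 | 0.828 |

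The last column uses SE = 3.53 × √(1 − R²) and compares with 0.809. For a factor that is already balanced the gain is smaller still, because the unadjusted test has power Φ((10 − 1.96 × 3.53)/(3.53 × √(1 − R²))), which is about 0.810 at 1% and 0.815 at 5%.

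**3. Site imbalance if site is not a stratum.** The documents give no site sizes or prevalences. Assumed: 82 patients per site, diabetes 20% to 40%, previous stroke 10% to 30%, blocks of 4, 6 or 8, and 4,000 simulated trials per scenario.

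| | Blocks by diabetes × stroke | Blocks by site × diabetes × stroke |
|---|---|---|
| Largest TEAM-minus-ETAU difference at a site, median | 8 | 2 |
| Same, 95th percentile | 18 | 6 |
| Difference of 10 or more at some site | 44% to 46% | under 0.1% |
| Overall arm-size difference, 95th percentile | 4 | 8 |

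If site totals vary at random instead of being fixed at 82, the 44% to 46% becomes about 41%.

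**4. What that imbalance does to H1.** Without site blocking, the largest between-arm difference in a site's share of patients is about 0.065 to 0.07 at the median and 0.14 to 0.15 at the 95th percentile. Suppose one site's mean BP change differs from the others by 5 mm Hg (assumed). The estimate then shifts by about 0.065 × 5 = 0.3 mm Hg at the median and 0.15 × 5 = 0.75 mm Hg at the 95th percentile, against an SE of 3.53.

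**5. Form of the terms.** H1 is a time-by-treatment contrast. A covariate or centre effect that is constant over time shifts a patient's readings equally at every visit and cancels from within-patient change. Diabetes, previous stroke and site therefore bear on H1 only if they enter with their time interactions. The plan does not say in what form its listed covariates enter.

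**The case against.** A reader might infer that randomisation ignores site. The text does not support this. It promises equal numbers within strata and, in addition, balance on two comorbidities, so an undefined set of strata could include site. The imbalance figures above apply only if it does not.

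A reader might also infer that the analysis ignores the randomisation factors altogether, or never accounts for site. Neither follows. Stroke history is a listed covariate, the list need not be exhaustive, and the sample-size model has a centre-level random effect. Site is missing only if the repeated-measures ANOVA is the primary analysis, and the documents leave that unsettled.

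The effect is also small. The error from omitting diabetes is conservative. Stable hospital differences in BP level cancel, as does a constant rater offset, since a single rater does all of a participant's assessments. A gap of 10 (46 against 36 of 82) still lets a site form several groups of 6 to 8.

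All of this limits the size of the point, but two gaps remain. Diabetes is named for balancing and is not named for H1. The Missing Data section could bring it in only as an auxiliary variable correlated above 0.40 with both missingness and the response. A correlation of 0.40 means R² = 0.16, well above the range considered here. And a centre random effect, if it is only an intercept, does not adjust for site differences in change.

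**Conclusion.** The point holds as a modest gap between design and analysis. Diabetes is balanced at randomisation and absent from the listed H1 covariates. Site is in the power model and absent from the described H1 analysis.

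Under an assumed R² of 1% to 5%, omitting diabetes makes the H1 standard error 0.5% to 2.6% too wide, and adjustment lifts power from 0.809 to at most 0.813 to 0.828. Those figures should not be read as the combined effect of diabetes and site, because the too-wide standard error applies only to factors that were balanced. For site, the exposure is a shift of roughly 0.3 to 0.75 mm Hg under an assumed 5 mm Hg difference in change at one hospital, and only if site is not a stratum.

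Nothing here suggests false-positive inflation, bias in the randomisation or an inadequate sample size. The case for acting is that the remedy is nearly free.

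**What to change.** 1. In Quantitative data Analysis, include diabetes, previous stroke and site as fixed terms in the H1 model, each with its time interaction. With only three sites, fixed terms are steadier than an estimated centre variance.
2. Make Quantitative data Analysis and Sample size calculations name the same primary model. Settle this before outcome data are examined by arm, including at the interim analysis planned when half the participants have completed 6 months.
3. In RCT Treatment randomization, define the strata and say whether site is one.
4. If site is not a stratum and the list can still be changed, generate it by site × diabetes × previous stroke (3 × 2 × 2 = 12 strata) with the same random blocks. If randomisation is under way, make the covariate change alone.

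Cost: diabetes status is already needed for the balancing and site is known, so items 1 to 3 are wording and a few model terms. Item 4 needs a new list and leaves some incomplete blocks. Under the assumptions above, it raises the 95th percentile of the overall arm-size difference from about 4 to 8 patients. Site stratification does not address correlation among patients treated in the same TEAM group, which is a separate matter.

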Aim 2: To conduct an RCT comparing efficacy of TEAM vs. enhanced treatment as usual (ETAU) in 246 Ugandans (TEAM, N= 123; ETAU, N= 123) at high risk for stroke. Phase 2 consists of an RCT using a Type 1 hybrid effectiveness-implementation design, which rigorously tests the clinical intervention and secondarily gathers data to inform subsequent implementation efforts and research. The RCT will evaluate key primary (systolic BP) and secondary (biological and behavioral) outcomes indicative of stroke risk. H1: Individuals in TEAM will have significantly reduced systolic BP compared to individuals randomized to ETAU. H2: Individuals randomized to TEAM will have greater reductions in serum cholesterol compared to ETAU. H3: Individuals with diabetes randomized to TEAM will have improved glycemic control as measured by serum HbA1c compared to ETAU. Secondary outcomes also include other biomarker variables, stroke knowledge and attitudes, medication adherence and health resource use. We will also explore associations of age, gender, urban vs. rural residential status and stroke history (prior vs. no previous stroke) on TEAM outcomes.

Aim 3: Identify barriers and facilitators to TEAM implementation in order to inform subsequent scale-up and spread using qualitative methods and guided by an implementation conceptual model. As with Aim 1, Aim 3 evaluation will be guided by an i-PARIHS framework. Finally, the project will grow research capacity in stroke risk reduction, training the next generation of brain health investigators in SSA. The project will help establish a sustainable infrastructure that will facilitate future scale-up of TEAM in Uganda. Taken together, the proposed project has substantial public health importance and will provide the prerequisite data and infrastructure needed to help with reducing stroke burden in Uganda and other LMIC countries across the globe.

Study Design

The proposed project is a prospective, randomized effectiveness-implementation trial of TargEted MAnageMent Intervention (TEAM. N= 123) vs enhanced treatment as usual (ETAU, N=123) in Ugandans who are at risk for stroke or have had a stroke within the last 5 years.

Study Procedures

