2.	At risk for stroke defined by the following: a.) High systolic BP defined as ≥ 140 mmHg assessed on at least 2 occasions at least 3 days apart and either criterion b or c as noted below: b.) At least 1 other modifiable stroke risk factor including: diabetes, hyperlipidemia, obesity, smoking, problem alcohol use or sedentary lifestyle. Problem alcohol use for screening purposes

	
will be assessed with questions on frequency, type of alcohol and quantity consumed. Participants will be classified as engaging in potential problem alcohol use if they exceed the recommended level for safe alcohol intake i.e. more than 3 drinks on average every time they drink, or if they undertook binge drinking (i.e. more than 3 drinks on one occasion in the one month preceding the evaluation).^{70, 71}
 
c.) History of stroke or transient ischemic attack within the past 5 years

3.	Able to participate in group sessions
	Inclusion Criteria for Care Partner participant
1.	Age range: from 18 to 90
2.	Able to participate in group sessions
	Inclusion Criteria for Peer Educator
1.	Age range: from 18 to 90
2.	
At risk for stroke defined by the following:
 
a.) High systolic BP defined as ≥ 140 mmHg assessed on at least 2 occasions at least 3 days apart and either criterion b or c as noted below:
 
b.) At least 1 other modifiable stroke risk factor including: diabetes, hyperlipidemia, obesity, smoking, problem alcohol use or sedentary lifestyle. Problem alcohol use for screening purposes will be assessed with questions on frequency, type of alcohol and quantity consumed.
 
Participants will be classified as engaging in potential problem alcohol use if they exceed the recommended level for safe alcohol intake i.e. more than 3 drinks on average every time they drink, or if they undertook binge drinking (i.e. more than 3 drinks on one occasion in the one month preceding the evaluation).^{70, 71}
 
c.) History of stroke or transient ischemic attack

3.	Able to participate in group sessions
	Inclusion Criteria for Peer Educator Care Partner
1.	Age range: from 18 to 90
2.	Able to participate in group sessions
	Inclusion Criteria for Clinic Staff
1.	Member of clinic and administrative staff (whether they referred participants to study or not) at the 3 sites (physicians, nurses, health workers, pharmacists).

	Exclusion Criteria for RCT participant
1.	Individuals who are unable or unwilling to provide written informed consent

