Feasibility and Fidelity: Attendance for each TEAM and ETAU contact will be recorded. Acceptability for each intervention will be assessed at 13 weeks with a brief self-rated survey. Following Fraser et al.,⁷⁸ fidelity to the TEAM intervention will be assessed quantitatively and qualitatively. Fidelity to TEAM processes, content and format will be evaluated by random attendance of 20% of sessions by non-interventionist study staff to determine if sessions covered relevant TEAM constructs and health practices as identified in the specific sessions as well as assessment of if written prompts were appropriately utilized, and if sufficient time was devoted to the question/answer/ comment session. Each fidelity dimension will be rated on a 1-10 scale using the same evaluation process as in the TEAM pilot.

Risks to Research Participants

Patients will not be compelled to participate in any way in the activities of the project. Participants will be free to withdraw from the project at any time without penalty. This study involves participating in surveys and completing a set of self-report instruments, along with qualitative interviews. All instruments have been utilized in outpatient research settings and are not associated with risks to patients.

The behavioral intervention intended to enhance self-management is not expected to increase risk to individuals. Because of the nature of group interaction, patient confidentiality cannot be guaranteed. However, the importance of respecting other group members' privacy will be stressed to all participants.

The risks to the participants will be primarily those of talking about some matters that they may find uncomfortable. All participants will have blood drawn twice, at baseline and at 6-month follow-up. There is minimal risk to blood draw. However, when a blood sample is taken, participants may experience temporary discomfort, bruising, and/or infection or blockage of the vein where the needle is put into their arm. On rare occasions, fainting may occur.

PEDs are not expected to incur risk, however in the unlikely event that participation in TEAM is experienced as stressful, appropriate measures will be taken by the on-site clinical members of the study to minimize burden or distress.

Potential Benefit to Research Participants

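### Diabetes is a balancing factor in the randomisation and defines the H3 population, but it is missing from the explanatory variables of the systolic BP model and so from the moderators

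*Combined protocol and SAP*

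**What the plan says.** The paragraph on RCT treatment randomization describes 1:1 allocation in randomly varying blocks of 4 to 8. The aim is that "equal numbers of TEAM and ETAU patients occur within strata" and that the arms are "balanced with respect to relevant comorbidity (diabetes and previous stroke".

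Under Quantitative data Analysis, the test of primary interest is treatment by time in systolic BP from baseline to 6 months, and "Explanatory variables will include age, gender, stroke history and rural vs. urban status". The Secondary outcomes paragraph takes its exploratory moderators from those explanatory variables. The exploratory factors listed under Aim 2 and under Study Procedures are the same four. Diabetes is in none of these lists.

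Diabetes does define the population of one of the three named hypotheses: "H3: Individuals with diabetes randomized to TEAM will have improved glycemic control as measured by serum HbA1c compared to ETAU". The analysis section then applies the same two-group, three-wave analysis to HbA1c without repeating the restriction to people with diabetes.

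**The concern.** Balancing the arms on a prognostic factor removes that factor's contribution to the chance difference between arms. A model that omits the factor does not credit this. It leaves the factor's variance in the residual, so the reported standard error is larger than the true one. The estimate stays unbiased, but the confidence interval is wider than it need be and the test runs below its nominal level.

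For H3 the stake is different. Everyone in that analysis has diabetes, so diabetes cannot be a covariate there. What matters is who counts as diabetic. Randomisation balances the group recorded as diabetic at allocation. The plan does not say that this is the group H3 will use, and no section defines diabetes by history, medication or HbA1c. That leaves the H3 analysis set open until after outcome data exist.

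**Working it through.** **Inputs from Sample size calculations:** SD 25.84, within-subject correlation 0.57, compound symmetry, difference 10 mm Hg, two-sided alpha 0.05, 123 per arm, 25% attrition, stated power 0.80.

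**Step 1: reproduce the stated power.** Read 25.84 as the SD at a single visit.
- SD of change = 25.84 × √(2 × (1 − 0.57)) = 23.96.
- Completers per arm = 123 × 0.75 = 92.25.
- SE of the difference = 23.96 × √(2/92.25) = 3.53.
- Power = Φ(10/3.53 − 1.96) = 0.809, which agrees with 0.80.

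Reading 25.84 as the SD of change gives 0.748, so the first reading is used. The centre random effect has no stated variance and is not modelled.

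**Step 2: effect of omitting diabetes.** Let R² be the share of variance in systolic BP *change* explained by diabetes. The documents do not give it, so a range is assumed, with exact balance on diabetes between arms.
- True SE = 3.53 × √(1 − R²). The model without diabetes reports 3.53.
- True type I error without diabetes = 2 × [1 − Φ(1.96/√(1 − R²))].
- Power without diabetes = Φ((10 − 1.96 × 3.53)/true SE).
- Power with diabetes = Φ(10/true SE − 1.96).

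| Assumed R² | Type I error, omitted | Power, omitted | Power, included | Loss (points) |
|---|---|---|---|---|
| 0 | 0.050 | 0.8090 | 0.8090 | 0 |
| 1% | 0.049 | 0.8102 | 0.8129 | 0.3 |
| 2% | 0.048 | 0.8114 | 0.8167 | 0.5 |
| 5% | 0.044 | 0.8151 | 0.8284 | 1.3 |
| 10% | 0.039 | 0.8216 | 0.8479 | 2.6 |

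**Step 3: which term helps.** The test is treatment by time. If people with diabetes have systolic BP that is higher by a constant amount at every visit, that difference cancels from within-person change, and a diabetes main effect barely moves the test. The gain in the table needs diabetes by time.

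**Step 4: size of the H3 group.** The documents give neither a sample size for H3 nor a diabetes prevalence. At an assumed prevalence of 20 to 30%, the participants remaining per arm are 123 × 0.75 × 0.20 = 18 to 123 × 0.75 × 0.30 = 28. In groups that small, moving a few people in or out is a visible change.

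**The case against.** The strongest reply is that the list of explanatory variables is not closed, the omission is conservative and unbiased, and the moderator analyses are labelled exploratory. The second and third points stand and limit the weight of this one. On the first, no section adds diabetes. The rule in Missing Data admits a covariate only if it correlates above 0.40 with both missingness and response (0.40² = 16% of variance), so it would bring diabetes in only by chance.

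A reader might infer more than the documents support:

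- **That the stroke stratum conflicts with the stroke-history variable.** It does not. The exploratory variable is "stroke history (prior vs. no previous stroke) on TEAM outcomes", the same concept as the balancing factor.
- **That the strata conflict with the entry criteria.** Criterion 2b names diabetes. Criterion 2c reads "History of stroke or transient ischemic attack within the past 5 years", which adds TIA and a time window, but a stratification factor need not equal an eligibility criterion. How a TIA-only patient or one with an older stroke is coded is not stated, so misclassification cannot be asserted. Recoding the stratum to match 2c would replace the sponsor's stated variable with a preference.
- **That diabetes status must shift between allocation and analysis because of when blood is taken.** "All participants will have blood drawn twice, at baseline and at 6-month follow-up", and allocation follows all screening and baseline procedures, so the first sample precedes it. Nothing shows that the H3 group differs from the stratum, or that its arm sizes are uncontrolled. Anyone in both groups stays balanced.
- **That the wrong population could be enrolled.** Study Design speaks of a trial "in Ugandans who are at risk for stroke or have had a stroke within the last 5 years", which is looser than criterion 2. The inclusion criteria set eligibility and require raised systolic BP of everyone, so the difference is editorial.

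**Conclusion.** The point holds in a limited form. Diabetes is balanced at randomisation, is not among the stated explanatory variables and is therefore not among the moderators. The consequence for H1 is small and in the safe direction: no bias, no change in sample size, true type I error of about 0.048 to 0.044, and about 0.5 to 1.3 points of power lost. These figures assume that diabetes explains 2 to 5% of the variance in systolic BP change, that balance on diabetes is exact among those analysed, and that 25.84 is a per-visit SD.

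For H3, the analysis set is not tied to the group that the randomisation balances. That is a gap in specification; it is not evidence that a different group will be used. The case for acting is that the remedy is nearly free, not that the current plan is invalid.

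**What to change.** - **H1 model:** add diabetes, as recorded at randomisation, and its interaction with time, alongside stroke history.
- **Moderators:** add diabetes to the exploratory list.
- **H3:** state in the analysis section that it is run in participants classified as diabetic at randomisation. Say how that classification is made, and keep it fixed whatever later HbA1c shows.

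The cost is one or two more model terms and some analysis wording, using data that stratified allocation already requires. The randomisation scheme does not change. The documents do not say how far the trial has progressed, so the wording should be settled before outcomes are examined by arm.
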